8.9.3.5 EQ-5D-5L Quality of Life questionnaire results at Baseline and Week 12/ET

The EQ-5D-5L Quality of Life (QOL) instrument is collected at Randomization/Baseline and Week 12/ET.

The EQ-5D-5L QOL instrument consists of 5 dimensions of quality of life (mobility, self care, usual activities, pain/discomfort, and anxiety/depression) and the EQ visual analogue (EQ VAS) measure of “how good or bad your health is today”.

For each of the 5 dimensions, subjects choose between 5 levels (no problems, slight problems, moderate problems, severe problems, and extreme problems). Answers are scored from 1 (no problems) to 5 (extreme problems). The EQ VAS is measured from 0 (“The worst health you can imagine”) to 100 (“The best health you can imagine”).

The EQ-5D-5L questionnaire is collected at Randomization/Baseline and Week 12/ET. Summaries of the number and percentage of subjects at each level in each dimension will be presented at the two time points. Summary statistics will be provided for the EQ VAS at Randomization/Baseline and Week 12/ET, and for change from Baseline to Week 12/ET.

8.9.4 Subgroups

The primary and secondary analyses will be performed for the following subgroups:

- Sex (male versus female)
- Age (< 65 versus \geq 65 years)
- Type 1 or Type 2 diabetes mellitus (presence versus absence at baseline)
- Baseline potassium category (4.3 to < 4.7 mEq/L versus 4.7 to 5.1 mEq/L) from central lab
- Region (Group A versus Group B)
- History of heart failure (presence versus absence at baseline)
- Baseline eGFR (< 30 versus \geq 30 mL/min/1.73 m²)

The test for interaction between treatment and a subgroup will be performed.

8.9.5 Exploratory Efficacy Analysis

7dHBP over time

Summaries of 7dHBP SBP/DBP will be provided at each visit and for change from Baseline, by treatment group. Summaries of change at each post-baseline time point will include only subjects who have non-missing values at baseline and at the post-baseline time point of interest.

Mean SBP/DBP and mean change from baseline will be presented graphically.

8.10 Safety Analyses

8.10.1 Adverse Events

AEs and SAEs will be coded to system organ class (SOC) and preferred term (PT) in accordance with MedDRA 18.1. Adverse event analyses will include only treatment-emergent AEs (TEAEs). A TEAE is defined as any AE that newly appeared or worsened in severity following initiation of study drug administration. If the onset date of an AE is missing, the AE will be considered treatment-emergent unless there is evidence to conclude that it is not. AE listings will include all AEs.

Central laboratory serum pregnancy tests will be done at S1 and Week 12/ET. Local urine pregnancy tests will be done at Randomization/Baseline. Pregnancy is not considered an AE but is reported separately (please see Protocol Amendment 2 Section 8.4 regarding Procedures for Reporting Pregnancy Exposure and Birth Events).

The incidence of TEAEs will be summarized by system organ class (SOC), preferred term (PT) and severity. For those TEAEs that occur more than once during the study period, the maximum severity will be used in the summary by severity.

Descriptive statistical summaries (frequencies and percentages) will be provided by treatment group for the followings:

- Overall summary of TEAEs, including summaries of severity, TEAEs related to study drug, SAEs, SAEs related to study drug, TEAEs leading to study drug modification and TEAEs leading to study drug discontinuation
- Summary of all TEAEs by SOC, PT and severity
- Summary of TEAEs related to study drug by SOC, PT, separately for spironolactone and patiromer/placebo
- Summary of TEAEs leading to study drug modification by SOC, PT, separately for spironolactone and patiromer/placebo
- Summary of TEAEs leading to early study drug discontinuation by SOC, PT, separately for spironolactone and patiromer/placebo

- Summary of SAEs by SOC, PT, and severity
- Summary of SAEs related to study drug by SOC, PT, separately for spironolactone and patiromer/placebo
- Summary of TEAEs of special interest (e.g. allergic reactions, gastrointestinal events, renal events)

A listing for all AEs will be provided, including verbatim term, PT, SOC, severity, whether serious, relationship to each study drug, onset and end date, action taken and outcome of event will be provided. Listings of SAEs and TEAEs leading to study drug modification and to early study drug discontinuation will be provided. Listings will also be provided for events of special interest.

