A comprehensive assessment of safety of patiromer for the treatment of hyperkalemia was conducted. A total number of 1099 subjects were exposed to at least one dose of patiromer and a pooled safety analysis was conducted in 666 subjects receiving patiromer and 49 subjects receiving placebo. Data from the overall safety population demonstrated that patiromer was well-tolerated. Adverse events (AEs) and serious adverse events (SAEs) were reported in 60.8% and 8.3% of subjects, respectively, of the overall safety population receiving patiromer for up to 52 weeks. Approximately 20% of subjects receiving patiromer experienced AEs considered related to study drug but no SAEs were considered drug related. The proportion of subjects discontinuing study drug due to an AE was relatively low at 9%, indicating the therapy was generally well tolerated in subjects, including those who were treated for up to 1 year in the long-term efficacy and safety Phase 2 Study RLY5016-205. Overall, the most common reported AEs were gastrointestinal in nature and predominantly were events of constipation and diarrhea. These events tended to occur early after treatment initiation, were mild to moderate in nature, occurred in less than 10% of subjects, were self-limited and typically did not require dose reductions or discontinuations. Hypokalemia AEs and measured potassium levels < 3.5 mEq/L did occur but were infrequent and none of these events were serious or associated with electrocardiogram (ECG) changes. AEs of chronic renal failure, acute renal failure and cardiac disorders events were also observed, however these events generally were not assessed as being attributable to patiromer but consistent with AEs expected in study population with a high burden of CKD, diabetes mellitus, HF, and coronary artery disease.

Refer to the current version of the Investigator's Brochure for a more detailed summary of these clinical studies (Investigator's Brochure, 2016).

1.1.2 *Spironolactone*

Spironolactone is a potent, nonselective, steroidal MRA that competitively inhibits aldosterone binding to the mineralocorticoid receptor (MR) and renders it transcriptionally inactive, thus antagonizing the genomic effects of aldosterone. It does not antagonize aldosterone-induced nongenomic renal and extrarenal effects (Tamargo, 2014).

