Since there are substantial differences in international guideline recommendations for target BP in CKD, Rossignol, et al. (Rossignol, 2015) recommend BP levels for defining resistant hypertension that are consistent with those of the general population (ie, office SBP ≥ 140 mmHg or diastolic blood pressure [DBP] ≥ 90 mmHg). Out of office blood pressure measurements have been shown to be more accurate compared with office BP measurements and can exclude white coat hypertension and masked hypertension, both common in patients with CKD. However, more recently, data suggest that automated office BP (AOBP) using an automatic oscillometric monitoring device without study staff present may have less variability; therefore, AOBP measurements will be used in this study for subject selection, treatment decisions, and the primary evaluation of BP effects, and target blood pressure for these patients will be 135/85 mmHg. Home blood pressure (HBP) measurements and subject-measured blood pressure (SMBP) performed at the study site by the patient using the HBP monitor will also be performed. Home blood pressure measurements may also improve adherence to medications by increasing patient involvement (Wolley, 2016).

In this study, the BP comparison of greatest interest will be the between group difference in change from baseline blood pressure which theoretically should reflect the difference in proportion of subjects remaining on spironolactone at Week 12. It is anticipated that a larger proportion of subjects in the placebo plus spironolactone group will meet spironolactone discontinuation thresholds for potassium during the treatment period. To insure the safety of these subjects without confounding the between group comparisons unduly, subjects randomized to the study will be limited to those with systolic AOBP from 135 to < 160 mmHg, who are less likely to require urgent treatment of hypertension should spironolactone be discontinued. All subjects who experience persistent systolic BP of 165 mmHg or greater may be treated with additional antihypertensive therapy chosen by the investigator.

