Throughout the Double-Blind Treatment Period, subjects who develop $K^+ \geq 5.5$ mEq/L that cannot be managed with blinded patiromer/placebo escalation according to the treatment algorithm (refer to Appendix B) will discontinue spironolactone and patiromer/placebo, but will remain in the study (refer to Appendix C) and complete all remaining scheduled visits. After discontinuation of spironolactone and patiromer/placebo, hyperkalemia may be treated using the standard of care per the Investigator's judgment.

Spironolactone treatment:

Spironolactone will be initiated for all randomized subjects on Day 1, at a dose of 25 mg taken orally QD. At Week 3, for subjects with AOBP SBP ≥ 120 mmHg and $K^+ \leq 5.1$ mEq/L, spironolactone will be increased to 50 mg QD. For subjects with $K^+ > 5.1$ mEq/L, 25 mg daily dose of spironolactone will be continued until the first subsequent visit when K^+ is ≤ 5.1 mEq/L (and AOBP SBP ≥ 120 mmHg), at which time spironolactone will be increased to 50 mg QD.

Subjects with AOBP SBP < 120 mmHg at the Week 3 Visit will continue their 25 mg daily dose, unless symptoms of hypotension are present with SBP < 120 mmHg, or if SBP is < 100 mmHg (Appendix C), in which case the spironolactone dose may be reduced to 25 mg every other day or discontinued altogether, at the discretion of the Investigator. Spironolactone may be reduced or discontinued for SBP < 100 mmHg. If spironolactone is discontinued, patiromer/placebo must be discontinued at the same time. These subjects will remain in the study and be followed per protocol.

Note: During all study visits, if a subject experiences symptoms of hypotension with AOBP SBP < 120 mmHg, or if SBP < 100 mmHg, spironolactone dose may be reduced (e.g., 25 mg every other day) or discontinued at the discretion of the Investigator.

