8 ADVERSE EVENT REPORTING

8.1 Definition of an Adverse Event

An AE is any untoward medical occurrence in a clinical investigation subject administered a pharmaceutical product and which does not necessarily have a causal relationship with this treatment (Clinical Safety Data Management, 1995). An AE can therefore be any unfavorable or unintended sign (including an abnormal laboratory finding), symptom, or disease temporally associated with the use of a medicinal (investigational) product, whether or not related to the medicinal (investigational) product. This includes: 1) any new medical condition, sign or symptom, clinically significant physical examination abnormality or newly diagnosed event that occurs during the AE reporting period (see Section 8.2.1), including signs or symptoms associated with an underlying condition that were not present prior to the AE reporting period; 2) a preexisting condition that has worsened in severity or frequency or changed in character after the subject signs the informed consent during the AE reporting period; and 3) complications

that occur as a result of protocol-mandated interventions. An AE can arise from any use of the investigational drug (e.g., off-label use, use in combination with another drug) and from any route of administration, formulation, or dose, including an overdose. It also includes any side effects, injury, toxicity or sensitivity reactions that may be experienced by a subject in this clinical trial.

Out of range laboratory results, ECGs, vital signs and other safety assessments will be considered AEs if they meet at least one of the following criteria:

- Associated with symptoms or lead to a diagnosis (in such case the symptom or diagnosis will be recorded as an AE)
- Lead to discontinuation of patiromer
- Required treatment or subject referral for further testing outside the protocol (repeat testing or titration are within protocol procedures)
- The Investigator or Relypsa considered the abnormality as clinically significant in its own right (e.g., asymptomatic creatinine kinase > 5000 IU/L)

For the purposes of this protocol, events that will not be considered AEs include:

- Anticipated fluctuating signs or symptoms of a pre-existing medical condition (e.g., tremor in a subject with Parkinson's disease; migraine episodes) that have not worsened in severity or frequency or changed in character during the AE reporting period

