All AEs will be recorded using the words of the subject (verbatim term) to describe the AE whenever possible. However, if the verbatim term is vague or ambiguous (e.g., cramps), the study staff will try to obtain clarification by asking a follow-up question (e.g., what kind of cramps?) and record the words the subject used to clarify the event (e.g., menstrual cramps, calf muscle cramps). Additionally, if the subject reports a group of symptoms that the Investigator uses to make a unifying diagnosis, the diagnosis will be recorded instead of the symptoms (e.g., rhinopharyngitis instead of runny nose, cough, sore throat and sneezing). If a diagnosis is unknown, signs and symptoms need to be recorded separately until a diagnosis is determined, at which time the diagnosis will be reported in lieu of the symptoms.

The following information will be captured for each AE: date of onset and resolution, outcome, severity (as defined in Section 8.2.3), seriousness criteria, Investigator’s causality assessment for the relatedness of the AE to the investigational drug, action taken with the investigational drug and treatments administered. Any treatment administered as a result of an AE will be recorded on the Concomitant Medication CRF and/or Surgical and Medical Procedure CRF as applicable.

8.2.6 *Data and Safety Monitoring Committee*

A Data and Safety Monitoring Committee (DSMC) will review laboratory and blood pressure data, all reports of AEs (including deaths from any cause), discontinuations from spironolactone and patiromer/placebo, withdrawals from the study, and other data as described in the DSMC Charter. The DSMC Charter will include a description of the scope of planned reviews. When reviewing data, including individual data, the DSMC may be unblinded to treatment assignment (patiromer or placebo). The DSMC will advise the Steering Committee regarding the need for changes in the conduct of the study as outlined in the DSMC Charter.

8.3 **Serious Adverse Events Reporting**

8.3.1 *SAE Notification*

The Investigator has the obligation to report each SAE to Relypsa or designee within **24 hours** of knowledge of the occurrence. Follow-up reports must be submitted in a timely fashion as additional information becomes available. If the Investigator learns of any SAE that occurred

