Appendix B: Patiromer/Placebo Titration

Patiromer/placebo will be taken at a starting dose of two packets once daily (QD). Based upon the treatment algorithm, patiromer/placebo will be increased in two-packet per day increments for local $K^+ > 5.1$ mEq/L in intervals of at least 1 week up to a maximum dose of six packets QD. For subjects with $K^+ < 4.0$ mEq/L, patiromer/placebo dose will be decreased by at least two packets. The minimum dose of patiromer/placebo is 0 packets.

Throughout the Double-Blind Treatment Period, subjects who develop $K^+ \geq 5.5$ mEq/L that cannot be managed with blinded patiromer/placebo escalation according to the treatment algorithm (refer to Figure 2) will discontinue spironolactone and patiromer/placebo, but will remain in the study (refer to Appendix C, Spironolactone Dosing) and complete all remaining scheduled visits. After discontinuation of spironolactone and patiromer/placebo, hyperkalemia may be treated using standard of care per the Investigator's judgment.

Figure 2 describes patiromer/placebo dosing adjustments by Visit and level of potassium.

Figure 2: Patiromer/Placebo Titration

K⁺ = potassium; max = maximum; QD = once daily.

^a After discontinuation of spironolactone and patiromer/placebo, hyperkalemia may be treated using standard of care per the Investigator’s judgment.

[figure not shown]
NOTE: All patiromer/placebo dose increases should be made no less than 1 week apart. At Week 12 all study treatments (patiromer/placebo and spironolactone) will be discontinued.

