6.2 Safety Endpoints

Safety endpoints will consist of:

- Adverse events, including newly observed clinically significant physical examination abnormalities and events of interest (e.g. gastrointestinal events, renal events)
- Clinical laboratory test results and changes over time, including Spironolactone level and NT-pro-BNP.

- Vital signs
- ECG findings and changes
- Reasons for discontinuing patiromer/placebo/spironolactone
- Deaths

Adverse events will be coded using MedDRA 18.1.

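### Linked stopping rules put potassium- and spironolactone-driven stops into the patiromer/placebo discontinuation total and the overview line, which tilts both aggregates in patiromer's favour

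*SAP*

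**What the plan says.** SAP 8.10.1 (Adverse Events) lists, among its descriptive summaries, a "Summary of TEAEs leading to early study drug discontinuation by SOC, PT, separately for spironolactone and patiromer/placebo". The first item in the same list is an overall summary that counts TEAEs leading to discontinuation of study drug, without saying which drug.

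The protocol links the two stops:

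- Protocol 3.1.2, under spironolactone treatment: "If spironolactone is discontinued, patiromer/placebo must be discontinued at the same time". The footnote to Figure 3 in Appendix C repeats this.
- Protocol Appendix B: subjects with K+ of 5.5 mEq/L or more that escalation cannot manage "will discontinue spironolactone and patiromer/placebo, but will remain in the study".
- Protocol 7.6: new potassium-related ECG changes with local K+ at or above 5.5 mEq/L also stop both drugs.

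Protocol 8.1 lists the conditions that turn an out-of-range laboratory value into an AE. One is that it "Lead to discontinuation of patiromer". No matching condition names spironolactone.

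Protocol 1.2 anticipates that "a larger proportion of subjects in the placebo plus spironolactone group will meet spironolactone discontinuation thresholds for potassium".

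On data capture, Protocol 8.2.5 records for each AE the "action taken with the investigational drug and treatments administered". SAP 6.2 names "Reasons for discontinuing patiromer/placebo/spironolactone" as a safety endpoint. SAP section 8 specifies no table for that endpoint; the only early-stopping reasons it tabulates (8.2) are reasons for leaving the study.

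**The concern.** A summary given separately for each drug suggests that the patiromer/placebo part describes how well the binder was tolerated. Under the linked rules it describes more than that. A placebo subject whose potassium cannot be controlled stops both drugs. The laboratory value then qualifies as an AE because the binder was stopped, and the subject counts towards patiromer/placebo discontinuation. That count reflects lack of potassium control, which is what the primary endpoint is meant to detect. It does not reflect intolerance of the packets.

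The overview line has the same problem. Every spironolactone stop is also a patiromer/placebo stop, so, if recording is complete, the subjects who stopped either drug are the subjects who stopped patiromer/placebo. Reporting that line by drug is necessary but not sufficient, because the patiromer/placebo part still contains the linked stops.

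At stake is the between-arm comparison of discontinuation for AEs on the investigational product. A reader who takes the total as a tolerability figure may conclude that patiromer was better tolerated than placebo when own-account stops point the other way.

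**Working it through.** **The plan's own figure.** The SAP gives no expected rate for this table. The nearest design figure is N = 280 for 90% power to detect a 20-point difference in remaining on spironolactone, two-sided alpha 0.05 (SAP 2.3 and 8.1). No arm-specific rates are stated. Assuming 40% vs 60%, the pooled-variance formula gives

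n = [1.960·√(2·0.5·0.5) + 1.2816·√(0.24 + 0.24)]² / 0.20² = (1.386 + 0.888)² / 0.04 ≈ 129.3,

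or 130 per arm (N = 260). With continuity correction,

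(129.3/4)·[1 + √(1 + 4/(129.3·0.20))]² ≈ 139.1,

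or 140 per arm (N = 280). The stated N reproduces, and the 20-point gap serves below as an anchor for linked stops.

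**Inputs for the illustration (placebo / patiromer).**

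- Linked stops h: 30% / 10%. The levels are assumed; the gap equals the design difference.
- Own-account stops t: 2% / 9%. The 2% is assumed. The 9% is the AE-discontinuation figure in Protocol 1.1.1, borrowed only as an illustrative rate.

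**Total.** With independent causes, total = 1 − (1 − h)(1 − t).

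- Placebo: 1 − 0.70 × 0.98 = 31.4% (about 44 of 140).
- Patiromer: 1 − 0.90 × 0.91 = 18.1% (about 25 of 140).
- Difference: 13.3 points in patiromer's favour.

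**Own-account stops as first cause.** With constant competing hazards, the share is total × ln(1 − t) / [ln(1 − h) + ln(1 − t)].

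- Placebo: 0.314 × 0.0202/0.3769 = 1.7%.
- Patiromer: 0.181 × 0.0943/0.1997 = 8.5%.
- Difference: 6.8 points against patiromer.

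Earlier stopping on placebo shortens time at risk, but here it only lowers the placebo figure from 2.0% to 1.7%.

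**Sensitivity of the total (placebo / patiromer, %).**

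| Linked stops | Own-account 2/9 | Own-account 3/6 | Own-account 2/12 |
|---|---|---|---|
| 56/0 | 56.9 / 9.0 | 57.3 / 6.0 | 56.9 / 12.0 |
| 40/20 | 41.2 / 27.2 | 41.8 / 24.8 | 41.2 / 29.6 |
| 30/10 | 31.4 / 18.1 | 32.1 / 15.4 | 31.4 / 20.8 |
| 25/5 | 26.5 / 13.5 | 27.2 / 10.7 | 26.5 / 16.4 |
| 20/10 | 21.6 / 18.1 | 22.4 / 15.4 | 21.6 / 20.8 |
| 15/10 | 16.7 / 18.1 | 17.5 / 15.4 | 16.7 / 20.8 |
| 10/5 | 11.8 / 13.5 | 12.7 / 10.7 | 11.8 / 16.4 |

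The 56/0 row takes the incidence of K+ above 5.5 mEq/L in the earlier heart failure study (Protocol 1.2). It is an upper scenario and not a stop rate. The total reverses in every row with a linked-stop gap of 10 points or more. With a 5-point gap it reverses only for own-account 3/6.

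**Break-even.** At 30/10 with 2% own-account stops on placebo, patiromer's own-account rate would have to exceed 1 − 0.70 × 0.98/0.90 = 23.8% before its total looked worse.

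**Incomplete recording.** If only a fraction f of linked stops is recorded as TEAEs leading to patiromer/placebo discontinuation, then at 30/10 and 2/9 the totals are equal when 0.98(1 − 0.3f) = 0.91(1 − 0.1f). This gives f = 0.07/0.203 ≈ 0.345, so reversal needs about 35% or more to be recorded.

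**The case against.** The strongest reply is that the planned table is by SOC and PT. Hyperkalemia falls on its own row and gastrointestinal events on theirs, and Protocol 1.1.1 describes patiromer's common AEs as mainly constipation and diarrhea. Those rows keep their direction in every scenario above. SAP 8.10.1 also plans related TEAEs and related SAEs separately for each drug, a special-interest summary that names gastrointestinal events, and listings with relationship and action taken. All of this stands. A reader might infer that the table as a whole will show patiromer as better tolerated when it is worse; the documents do not support that. Only aggregates can reverse, and the SAP does not explicitly define a total row for this table.

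Nor do the documents call this the main discontinuation figure. The summaries are descriptive, and as a count of what happened a linked stop is correctly included.

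The inputs can also be challenged. The 20-point difference belongs to an endpoint that counts stops and withdrawals for any reason. The 9% covers all AE discontinuations in earlier studies of up to one year. Both are borrowed, and the remaining rates are assumed.

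Finally, the coupling is explicit for hyperkalemia and hypotension. For stops driven by eGFR it rests on the general sentence and the Figure 3 footnote. Whether each linked stop reaches the table depends on how sites record the action taken for each drug.

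The reply does not supply the missing figure. Subjects can have several terms, so adding rows does not give a subject-level own-account total. Renal, hypotension and potassium terms can belong to either kind of stop. Relatedness is a different question from why a drug was stopped, and listings are not a between-arm summary.

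**Conclusion.** The point holds for two aggregates: any all-TEAE total for patiromer/placebo discontinuation, and the overview line. Read as tolerability, both are tilted in patiromer's favour by stops that the protocol expects more often on placebo. At 30/10 linked and 2/9 own-account stops, an own-account disadvantage of 6.8 points appears as an advantage of 13.3 points. Reversal is not certain. It fails at 15/10 and 10/5 with 2/9, and at 30/10 it needs about 35% of linked stops to be recorded in this category.

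The size rests on assumed rates and independent causes; the direction rests on the protocol's own expectation about potassium stops. The point does not extend to the individual SOC/PT rows or the drug-specific relatedness tables, and it does not show that the planned counts are wrong. It is a low-cost improvement to reporting.

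**What to change.** In SAP 8.10.1:

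1. Report the overview line on TEAEs leading to discontinuation separately for spironolactone and patiromer/placebo.
2. Show the patiromer/placebo discontinuation total split into (a) stops for a TEAE on patiromer/placebo's own account and (b) stops required by the potassium rule or by a spironolactone stop.
3. Classify from the action taken for each AE and the reasons for discontinuing each drug. If the eCRF does not mark linked stops, fix a blinded classification rule before database lock.
4. State that (a) is the tolerability comparison.

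The SOC/PT table can stay as planned, and no stopping rule changes. The cost is SAP wording, one extra table and some judgement where a stop has more than one cause. The patiromer figure may also look less favourable than the undivided total.
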